9.1 Safety Analysis Population (SP)

The safety analysis population includes all enrolled subjects who receive at least one dose of study drug. The safety analysis population is used for evaluating subject characteristics, treatment administration, safety endpoints and efficacy analyses related to PFS and OS.

9.2 Response Evaluable Population (REP)

The response evaluable population includes all subjects in the safety analysis population who have an adequate baseline disease assessment and at least one post-baseline disease assessment. The response-evaluable population is used for efficacy analyses related to objective response, including objective response rate (ORR), TTR, and DOR.

10. General Statistical Considerations

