2.2 Secondary Objectives

2.2.1 Part A – CX-2009 Monotherapy: Every 21-Day Dosing Regimen

The secondary objectives of Part A are to determine the following in subjects treated with CX-2009 every 21 days:

- Evaluate preliminary efficacy in subjects treated with CX-2009 as monotherapy on the basis of:
 - ORR by the RECIST Version 1.1;
 - Time to tumor response (TTR);
 - Duration of response (DOR);
 - PFS; and
 - Overall survival (OS);
- Characterize the pharmacokinetics (PK) of CX-2009 with respect to the following analytes:
 - Intact CX-2009 (referring to the prodrug form of CX-2009 ± DM4);
 - Total CX-2009 (intact and activated forms of CX-2009 ± DM4);
 - Total CX-2009-conjugated DM4 (antibody conjugated-DM4);
 - Free DM4; and
 - DM4-Me - a DM4 metabolite with potent cytotoxic activity; and
- Assess the incidence of antidrug antibody (ADA) formation to CX-2009.

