9.1 Populations

For assessment of MTD/RP2D, the population will be based on subjects who are evaluable for DLT determination (a “DLT-evaluable” subject is defined as having received at least 1 dose of CX-2009 (or CX-2009 and CX-072) and completed the full DLT observation period (either 21 or 28 days depending on the schedule) or a subject who has withdrawn from the study drug due to a drug-related toxicity. Subjects who are not DLT evaluable may be replaced in the cohort.

For assessment of efficacy (Parts B, C2, D2 and E2), subjects must have undergone at least 1 on-study imaging assessment. Subjects who die prior to his/her first on-study scan will not be counted as evaluable for this assessment.

The efficacy evaluable group for Parts D2 and E2 will include only those subjects who are determined to be PD-L1 positive.

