9.2 Other Statistical Analyses

Statistical assessments/methods for safety, efficacy, PK/PD, and immunogenicity are found in Section 11 of the Core. In instances where the statistical analysis plan (SAP) might contradict the analyses specified in the Core, the SAP supersedes the Core.

Available data from Part A2 will be pooled with data from Part A by dose. In addition, efficacy data from Part A2 may be analyzed separately. The relationship between dose and safety/efficacy may be explored. Analyses by dose may be conducted for, but not limited to, the following endpoints: frequency of AEs of special interest, ORR, and percent reduction in tumor burden by dose. A generalized linear model may be used to adjust for covariates or to model the relationship. Because of the limited number of subjects, the above analyses will be conducted if data warrant.

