11. STATISTICAL PLAN AND ANALYSIS

Analyses common to the modules are described in the Common Core Document. Analyses specific to a Protocol Module will be described in a module-specific statistical analysis plan (SAP).

Descriptive summaries will be provided. For continuous measures, these include mean, median, standard deviation, and range. For categorical measures, these include counts and percentages.

The safety analysis population includes all enrolled subjects who receive at least one dose of study drug. The safety analysis population is used for evaluating subject characteristics, treatment administration, safety endpoints, and efficacy analyses related to PFS and OS.

The response evaluable population includes all subjects in the safety analysis population who have an adequate baseline disease assessment. The response-evaluable population is used for efficacy analyses related to objective response, including objective response rate (ORR), TTR, and DOR.

Analyses may be presented by cancer type, treatment regimen, and dose, when applicable.

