| q 21 days | every 21 days |
| RECIST | Response Evaluation Criteria in Solid Tumors |

| Abbreviation | Definition |
|---------------------|---|
| REP | response evaluable population |
| RP2D | recommended Phase 2 dose |
| SAE | serious adverse event |
| SAP | statistical analysis plan |
| SD | standard deviation |
| SD | stable disease |
| SOC | system organ class |
| SP | safety population |
| SRC | safety review committee |
| TEAE | treatment-emergent adverse event |
| TESAE | treatment-emergent serious adverse event |
| TMTB | total measured tumor burden |
| TTR | time to response |
| WHODrug | World Health Organization Drug Dictionary |

1. Purpose

This Statistical Analysis Plan (SAP) describes the statistical methodology and data handling for CytomX Therapeutics, Inc. protocol module number CTMX-M-2009-001 (A Phase 1-2, Open-Label, Dose-Finding, Proof of Concept, First-in-Human Study to Evaluate the Safety, Tolerability, Pharmacokinetics, and Pharmacodynamics of CX-2009 in Adults with Metastatic or Locally Advanced Unresectable Solid Tumors). The analysis specified in this SAP will be used to support safety review committee (SRC) and data and safety monitoring board (DSMB) analyses, publications, and FDA submissions. The proposed analyses may not be carried out if the sample size is not adequate.

The ICH guideline E3 "Structure and Content of Clinical Study Reports" was used as a guide to the writing of the plan.

This SAP is based on the following study documents:

- Protocol Core Amendment 01, 11 November 2016
- Protocol Module Amendment 06, 09 August 2017,
- Protocol Substudy V1.0, 04 May 2018
- Annotated Case Report Forms

The enrollment in CTMX-M-2009-001 was stopped by sponsor decision as of 07 July 2020, with a final enrollment of XX subjects into Parts A, A2, B, and C1.

2. Study Population

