4.2 Subject Eligibility and Enrollment

[figure not shown]
At the time of the sponsor decision to stop enrollment into the study, there were 99 subjects enrolled and treated in the study: 37 in Part A, 39 in Part A2, 10 in the mTPI-2 cohort, 3 in Part B, and 10 in Part C1.

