13.1.1 Primary Efficacy Endpoint

The ORR is the primary efficacy endpoint. For solid tumors, response evaluation will be based on the RECIST criteria (v1.1) and ORR is defined as the proportion of subjects with complete response (CR) or partial response (PR) on two consecutive tumor assessments with scan dates at least 4 weeks apart according to RECIST (RECIST v1.1).

The primary efficacy analysis will be based on the REP. Exact 2-sided 95% Cis (using the Clopper-Pearson method) will be calculated for all proportion estimates.

A listing of tumor data including total tumor burden, RECIST v1.1 response assessments (target lesion evaluation, non-target lesion evaluation, and overall subject response) will be provided.

Response Assessment and Best Overall Response – RECIST v1.1

Efficacy outcomes will be summarized by dose level and by cancer type using RECIST v1.1 among the REP. The overall number of subjects for each dose; and the number, proportion, and 95% exact 2-sided CI (using the Clopper-Pearson method) of confirmed CR and PR, unconfirmed CR and PR, SD, PD, not evaluable (NE), overall response (CR + PR), disease control (CR + PR + SD) will be calculated. A summary table of the above response assessments by part using RECIST v1.1 among the REP will be provided. A swim lane plot of response assessment status over time using RECIST v1.1 will be produced.

The best overall response is the best response recorded from the start of study treatment until the end of treatment taking into account any requirement for confirmation. If the best overall response is determined before the end of treatment (e.g., for an interim data cut), then it is the best response recorded from the start of study treatment until the date of the data cut.

When no imaging/measurement is done at all at a particular time point, the subject is not evaluable (NE) at that time point. If only a subset of lesion measurements are made at an assessment, usually the case is also considered NE at that time point, unless a convincing argument can be made that the contribution of the individual missing lesion(s) would not change the assigned time point response (as may happen in the case of an assessment of PD).

Complete or partial responses may be claimed only if the criteria for each are met at a subsequent time point as specified in the protocol (i.e., ~8 weeks later and no

earlier than 4 weeks later). In this circumstance, the best overall response can be interpreted as in Table 1.

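### SAP 9.2 adds a post-baseline assessment to the Core's response-evaluable definition in every part without a reason; response rates can then rise or stay the same, but not fall

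*SAP*

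**What the plan says.** Core section 11 reads: "The response evaluable population includes all subjects in the safety analysis population who have an adequate baseline disease assessment". It asks for nothing after baseline.

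SAP 9.2 takes the same population and adds a second condition, limiting it to subjects "who have an adequate baseline disease assessment and at least one post-baseline disease assessment". It does not restrict this to any part and does not explain it. SAP 13.1.1 then states: "The primary efficacy analysis will be based on the REP". The same set carries disease control (13.1.1) and CBR16/24 (13.1.2). PFS and OS use the safety population (SAP 9.1).

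The Module (the main Protocol) has a similar condition in section 9.1, limited to the expansion parts: "For assessment of efficacy (Parts B, C2, D2 and E2), subjects must have undergone at least 1 on-study imaging assessment". It adds that a death before the first on-study scan makes the subject not evaluable for this purpose.

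On precedence, Module 9.2 says: "In instances where the statistical analysis plan (SAP) might contradict the analyses specified in the Core, the SAP supersedes the Core". The SAP lists as its basis "Protocol Module Amendment 06, 09 August 2017". That version is not among the documents. The supplied Module is a different one: it has nine parts, while SAP 4.1 describes seven.

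SAP 4.2 records that "there were 99 subjects enrolled and treated in the study: 37 in Part A, 39 in Part A2, 10 in the mTPI-2 cohort", with 3 more in Part B and 10 in Part C1. In Part A, ORR falls under a secondary objective, worded "Evaluate preliminary efficacy in subjects treated with CX-2009 as monotherapy on the basis of" a list that begins with ORR (Module 2.2.1). Parts A2 and C1 are the same. Only Part B, among the enrolled parts, has ORR as a primary objective.

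**The concern.** Membership of the SAP's set depends on something that happens after treatment starts. Whether a subject reaches a first scan can be linked to outcome: early death, rapid clinical decline and early withdrawal all prevent it. The first scheduled scan is at 8 (±1) weeks (Module Appendix B), and median exposure at the November 2019 data lock was 7.3 weeks (Module 1.3.4). A scan at the end-of-treatment visit recovers some early stoppers, but not those who die first. Some unassessed subjects are therefore plausible, although none is documented.

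The SAP also treats the same subject in two ways. Table 3 counts a death before the first disease assessment as a PFS event, while SAP 9.2 drops that subject from ORR. A subject whose only scan is not evaluable stays in the denominator as a non-responder; one who died before scanning does not.

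At stake is a set of response rates, shown by dose level and cancer type and intended for publications and submissions (SAP 1), on a denominator that can err in only one direction.

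**Working it through.** **The plan's own figures.** Module 9 gives 8 of 40 as 20% with a 90% CI of 10% to 33%. The exact (Clopper-Pearson) interval is 10.4% to 33.2%, so it reproduces. The interim percentages in Module 1.3.4.2 also reproduce: 2/92 = 2.2%, 6/92 = 6.5%, 21/92 = 22.8%.

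**Where the condition is additional to the supplied Module.** From SAP 4.2: 37 (A) + 39 (A2) + 10 (mTPI-2) + 10 (C1) = 96; adding 3 (B) gives 99. Module 9.1 covers only the 3 in Part B. Whether Amendment 06 had the same limit cannot be checked.

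**Direction.** Let x be the numerator, n the Core denominator and k the number with no post-baseline assessment. A CR or PR needs a post-baseline assessment, and SD must be met at least once after entry, at 7 weeks or later (SAP 13.1.1). None of the k subjects is in x for ORR, disease control, CBR16 or CBR24.

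- Core rate = x/n; SAP rate = x/(n − k).
- Ratio = n/(n − k) = 1/(1 − d), with d = k/n.
- The rate is unchanged if k = 0 or x = 0. Otherwise it rises. It cannot fall.

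For assumed d of 5%, 10%, 15% and 20%, the ratio is 1.05, 1.11, 1.18 and 1.25.

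**What the interim data say about k.** The 92 response-evaluable subjects (Module 1.3.4.2) equal the 92 with safety data (1.3.4.1). They also equal the enrolment reported to that point: 47 in Part A (3.2) + 39 in A2 (3.4) + 6 in C1 (1.3.4.1) = 92. Either the Core definition was used, and k is unknown, or the restricted definition was used and k was 0. The text does not say which.

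**Illustration, on the first reading only.** The numerators are 2 confirmed PR, 2 + 6 = 8 any PR, and 2 + 6 + 21 = 29 PR or SD (categories assumed exclusive). Confirmed and any-PR rates are both shown because SAP 13.1.1 waives confirmation in Parts A and A2. The values of k are assumptions. Intervals are exact 95%.

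| Numerator | k = 0 (n = 92) | k = 5 (87) | k = 9 (83) | k = 18 (74) |
|---|---|---|---|---|
| 2 confirmed PR | 2.2% (0.3–7.6) | 2.3% | 2.4% | 2.7% (0.3–9.4) |
| 8 any PR | 8.7% (3.8–16.4) | 9.2% | 9.6% | 10.8% (4.8–20.2) |
| 29 PR or SD | 31.5% (22.2–42.0) | 33.3% | 34.9% | 39.2% (28.0–51.2) |

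If the 92 is already the restricted set, these columns remove subjects twice and do not apply.

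**Dose groups.** With the interim group sizes in Module 1.3.4.1, one unassessed subject multiplies a non-zero rate by 8/7 = 1.14 at 10 mg/kg, 9/8 = 1.13 at 9 mg/kg and 22/21 = 1.05 at 8 mg/kg, all every 21 days. The documents give no responder counts for these groups. With none, the rate is 0% either way.

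**The case against.** The strongest answer is that the SAP made a choice open to it. The Core is a generic programme document that leaves module-specific analyses to the SAP, and the Module gives the SAP precedence over it. Extending the Module's Part B condition to the parts pooled with Part B yields a single definition across the dose tables. All of this stands. A reader might infer that the SAP breaches the Protocol; the precedence clause and the missing Amendment 06 do not allow that conclusion.

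A second answer is that little is hidden. Early deaths still count in PFS and OS. SAP 11.1 reports the number in each analysis population and the discontinuation reasons, so a reader can recompute a rate over all treated subjects, and an exact interval from it. This also stands in large part. It does not separate a missing baseline from a missing post-baseline assessment, or give the reason for the missing assessment.

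A third answer concerns the remedy. The precedence clause names the Core, not the Module. Module 9.1 itself excludes Part B subjects with no on-study scan, so a reader might infer that the SAP could simply impose the Core definition everywhere. For Part B, the documents do not support that.

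A reader might also infer that reported rates are inflated, or that the set was chosen for its effect, since enrolment had stopped when this SAP was written. The first is not shown, because the number unassessed may be zero. Nothing in the documents supports the second.

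**Conclusion.** The point holds as a minor one. SAP 9.2 is narrower than the Core definition, applies to all parts and gives no reason. What it removes can only be subjects outside the numerator, so ORR, disease control and CBR16/24 can rise or stay the same. They do not change if every subject was assessed, or in a group with nobody in the numerator. The direction follows from the definitions and needs no assumption.

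The size rests entirely on an assumed number of unassessed subjects. Even with 18 of 92, the any-PR rate moves by about 2 percentage points (8.7% to 10.8%), well inside its interval of 3.8% to 16.4%. Severity is minor because enrolment has stopped, Part B holds 3 subjects, and the SAP states no ORR test or threshold. The reasons to act are the one-way direction and the mismatch with the PFS rule.

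**What to change.** Change the SAP only.

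- **Parts A (including mTPI-2), A2 and C1:** use the Core definition for ORR, disease control and CBR16/24. State that a subject with no post-baseline disease assessment for any reason, including death, counts as a non-responder with best overall response NE.
- **Part B:** keep the Module 9.1 evaluable set as the main analysis and report the Core-set result beside it. This leaves the Module's rule in force.
- **Pooled A/A2/B dose tables:** show them on both sets, each labelled and with exact confidence intervals.
- **Reporting:** give the number of subjects with no post-baseline assessment, with reasons, by dose level and cancer type.

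The cost is some SAP text and one repeat of the response tables. No new data are needed, and the tables already have an NE category. Rates in Parts A, A2 and C1 may come out slightly lower; if every subject was assessed, nothing changes.

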10.1 General Statistical Methodology

Data will be analyzed using SAS (Version 9.4 or higher). All consented subjects are identified by an 8-digit Subject Number where the first four digits represent site and the last four digits are the sequential enrollment within a site (e.g. 1234-0001).

Descriptive statistics will be tabulated as follows:

- Categorical data will be summarized in contingency tables presenting frequencies and percentages.
- Continuous data will be summarized using number of non-missing values (n), mean, median, standard deviation, and median and range values. Where relevant, Q1 and Q3 may be presented.

The tables will be created by dose level and by cancer type, unless otherwise specified. For tables by dose level, all available data from Parts A, A2, and B will be pooled with ≤ 2 mg/kg presented as a single dose group and 4, 5, 6, 7, 8, 9, 10 mg/kg presented as separate dose groups; Part C1 dosing 4 mg/kg Q2W and 6

mg/kg Q2W will also be presented as separate dose groups. Data from planned, protocol-specified visits and unplanned visits will be included in listings, unless otherwise noted. Baseline tables will contain a total column when appropriate.

10.1.1 Handling of Missing Data

All data will be analyzed as they were collected in the database. Missing data, other than as described in Section 0, will not be imputed.

10.1.2 Derived and Computed Variables

The following derived and computed variables have been initially identified as important for pre-specified and exploratory analyses. Additional computed variables may be required to aid in analysis.

Missing Date Components of AEs, Concomitant Medications (including Prior Cancer Treatments), and Medical History

Every attempt will be made to obtain complete dates for any AEs, CMs, and Medical History; however, in the case of incomplete dates, the missing Day, Month or Year will be represented in listings as "UN", "UNK" or "UNKN", respectively. Missing Hour or Minute in times will be represented as "UN".

Missing date components for AEs, CMs, and Medical History will not be imputed; however, AEs with incomplete start dates (and times, in the case of infusion-related reactions) will be attributed to treatment according to the following algorithm:

- Only the year is reported: If the year is after or the same as the day of the first dose, the event will be considered treatment-emergent.
- Only the month and year are reported: If the month is after or the same as the day of the first dose, event will be considered treatment-emergent.
- Only the time is missing: If the event occurred on or after the day of the first dose in the treatment period, then the event will be considered treatment-emergent.

Dates with missing day values will be imputed to the 15th of the month when calculating time since the last prior cancer regimen or procedure. If a date is missing both day and month values, then the date will not be imputed and the prior cancer regimen or procedure will not be considered for selection as the last.

Study Days Relative to First Infusion of Study Medication

Study Day 1 is the day of the first infusion of CX-2009 (for subjects enrolled only to the main CTMX-M-2009-001 study) or the day of the first treatment with Zr-CX-2009 (for subjects enrolled to the CTMX-M-2009-001 imaging substudy); negative Study Days occur prior to first infusion of study treatment; and positive Study Days are those after the first study treatment – e.g., Study Day -1 is the day immediately preceding the first study treatment, Study Day 2 is the day immediately following the first study treatment.

Time on Study

Time on study (months) is calculated as the study termination date minus the first infusion date (+1) – this value is divided by 30.4375 to obtain the time in months. If the study termination date is missing, the data cutoff date will be used.

Time Since Prior Regimens or Procedures

Time since prior regimens or procedures (weeks) is calculated as the first infusion date minus the end date of the last prior (relative to study) regimen or procedure (+1) – this value is divided by 7 to obtain the time in weeks. Regimen or procedure end dates will be imputed to the 15th of the month when only the month and year are reported. If only the year is reported, then end date will not be imputed and the regimen or procedure will not be eligible for selection as the last prior regimen or procedure.

Time Since Initial Histopathological Diagnosis

Time since initial histopathological diagnosis (years) is calculated as the date of informed consent minus the date of the initial histopathological diagnosis (+1) – this value is divided by 365.25 to obtain the time in years.

Time Since Most Recent Disease Recurrence/Progression

Time since most recent disease recurrence/progression (years) is calculated as the date of informed consent minus the date of the most recent disease recurrence/progression (+1) – this value is divided by 365.25 to obtain the time in years.

AEs with Missing Relationship

Every attempt will be made to obtain complete information for AEs regarding relationship(s); however, in the case of missing data:

- AEs with missing relationship designations will be considered “Related” to study treatment provided the AE onset date/time occurs on or after the initial dose of CX-2009 was initiated.

Duration of Treatment

Duration of treatment for CX-2009 will be derived by subtracting the start date of the first infusion from the stop date of the last infusion (+1) - this value is divided by 30.4375 to obtain the time in months.

Percent of Infusion

The percent of each dose received will be calculated using the following formula rounded to one decimal place:

$$\text{Percent of Dose} = \frac{\text{Total Dose of Study Medication Administered} \times 100}{\text{Total Planned Dose of Study Medication}}$$

Duration of Infusion (min)

Duration of infusion in minutes will be derived by subtracting the Infusion Start Time from the Infusion Stop Time.

Laboratory Values with < or > Inequality Symbols

Some continuous laboratory data include “<” or “>” symbols. Data will be presented in listings with their inequality symbol; however, for tabulation of summary statistics of safety laboratory results, the number associated with the inequality sign will be used for statistical calculations.

Definition of Baseline

Unless otherwise specified, a baseline measurement will be taken as the last non-missing value prior to the start of study treatment.

